## 3.0 BACKGROUND AND SIGNIFICANCE

### 3.1 Background and Scientific Rationale

We have discovered that COVID-19 patients with high plasma interleukin (IL)-13 levels have a significantly greater risk of needing mechanical ventilation. IL-13, which signals through the receptor IL-4R $\alpha$  along with the closely related cytokine IL-4, is involved in eosinophilic inflammation, mucous secretion, goblet cell metaplasia and fibrosis, and has been regularly implicated in airway hyperresponsiveness and atopic disease. We additionally found that neutralization of IL-13 in K18-hACE2 C57Bl/6J mice protected the animals from severe infection with SARS-CoV-2, as evidenced by reduced clinical score, weight loss and mortality. The association of IL-13 along with other effectors of type 2 immunity with respiratory failure from COVID-19 has also been demonstrated in other observation studies. These findings established mechanistic and biologic plausibility for IL-13 as a driver of pulmonary injury in COVID-19.

RNA-seq analysis of whole lung tissue taken from infected mice who underwent IL-13 neutralization revealed the most downregulated gene to be Has1, which encodes a synthase responsible for hyaluronan (HA) production, a polysaccharide apart of the extracellular matrix that has previously been implicated in other inflammatory pulmonary diseases. This was mechanistically further supported by an increase in HA deposition in human and mouse lung with SARS-CoV-2 infection. Additionally, neutralization of the HA receptor, CD44, led to improved survival. As HA has been proposed previously in asthma as a potential culprit in airway remodeling, this led to the hypothesis that HA, as a downstream effector of IL-13, may be involved in pulmonary dysfunction post recovery from COVID-19.

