 - Moderate illness: Individuals who show evidence of lower respiratory disease during clinical assessment or imaging and who have saturation of oxygen $\text{SpO}_2 \geq 94\%$ on room air at sea level.
 - Severe illness: Individuals who have $\text{SpO}_2 < 94\%$ on room air at sea level, a ratio of

arterial partial pressure of oxygen to fraction of inspired oxygen ($\text{PaO}_2/\text{FiO}_2$) <300 mm Hg, respiratory frequency >30 breaths/min, or lung infiltrates $>50\%$.

- Patient and/or legally authorized representative is willing and able to provide written informed consent and comply with all protocol requirements.
- Patients with hematologic malignancies or solid tumors are eligible.
- Patients with autoimmune disorders are eligible.
- Patients with immunodeficiency and organ or stem cell transplant recipients are eligible.
- Patients with acute or chronic renal injury/failure are eligible.
- Patients with neutropenia/lymphopenia are eligible.
- Patients with elevated liver function tests are eligible.
- Women who are not taking contraception are eligible.
- Patients who are currently or have recently received steroids and/or remdesivir are eligible.
- Patient agrees to not participate in another clinical trial for the treatment of COVID-19 through end of study period.

Exclusion Criteria

- Patients who do not require inpatient admission for COVID-19 infection.
- Patients who require invasive mechanical ventilation at time of enrollment.
- A pre-existing condition or use of a medication that, in the opinion of the site investigator, may place the individual at a substantially increased risk due to study participation.
- Pregnancy or breast feeding (lactating women who agree to discard breast milk from day 1 until two weeks after the last study product is given are not excluded).
- Allergy to Dupilumab or its excipients.
- Current acute parasitic helminth infection or history of chronic parasitic infection.
- History of ocular scleritis, uveitis, keratitis or recent (<6 months) eye injury (chemical or traumatic), infection or vascular occlusion.
- Have received any live vaccine (that is, live attenuated) within 4 weeks before screening, or intend to receive a live vaccine (or live attenuated) during the study. *Note: Use of non-live (inactivated) vaccinations is allowed for all subjects.*

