2.0 Outcomes

2.1 Primary outcome: The primary efficacy endpoint of this double-blind, placebo-controlled phase IIa trial is a binary indicator for whether a patient would be alive and free of invasive mechanical ventilation at 28 days. The outcome will be summarized as the proportion of patients alive and free of invasive mechanical ventilation at 28 days in those receiving dupilumab in addition to standard of care (treatment arm) compared to those receiving solely standard of care management (placebo arm).

2.2 Secondary outcomes:

2.2.1 Eosinophilia as the safety outcome: The safety endpoint of this study is a binary indicator for whether a patient would have eosinophilia, which is defined as an absolute eosinophil count $> 0.6 \text{ k}/\mu\text{l}$ at ≥ 1 measurement throughout the study period. The outcome will be summarized as the proportion of patients with eosinophilia for treatment arm and placebo arm respectively. Complete blood counts with differentials

and complete metabolic panels will be measured on Day 0, 2, 5, 7, 14, 28 and 60. Day 7, 28 and 60 optional, although recommended, if patient discharged within the time frame.

2.2.2 **Other secondary safety and efficacy outcomes:**

- Cumulative incidence (defined as number of new events divided by the total number of individuals in the population at risk for the time interval) of grade 3 and 4 adverse events, serious adverse events or death including: injection site reactions, eye/eyelid inflammation, conjunctivitis, oropharyngeal pain, insomnia, tooth ache, gastritis, arthralgia, bacterial pneumonia, herpes viral infection, hypereosinophilic syndrome, hypersensitivity reaction.
- Prevalence of B.1.1.7 and B.1.351 and other SARS-CoV-2 lineages in study cohort: Day 0.
- Plasma total Immunoglobulin E (IgE) levels: Day 0 and 14.
- Plasma inflammatory markers (C-reactive protein and ferritin): Day 0, 7 and 14. Day 7 optional if patient discharged.
- Plasma cytokine levels including TARC (CCL17), YKL40, eotaxin 3 (CCL26), IL-13, IL-4, Arg1, Hyaluronan, soluble ST2: Day 0, 2, 5, 7, 14, and 28. Day 7 and 28 optional if patient discharged.
- Change in PaO₂/SaO₂ to FiO₂ ratio: Day 0, 2, 5, 7 (if patient remains inpatient throughout)
- All-cause mortality rate at 28 days.
- Hospital length of stay (LOS)
- ICU LOS
- Proportion of patients alive and free of invasive respiratory failure at 28 days.
- Proportion of patients alive and free of invasive mechanical ventilation at 60 days.

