5.1 General analysis strategy: The difference between dupilumab and placebo arms in outcome measures will be primarily analyzed under ITT principle, regardless of patient's use of rescue medications, protocol violations, or investigational product discontinuation. The difference will be tested initially with Chi-square for categorical measures (e.g., the primary efficacy endpoint) and two-sample t-test or Wilcoxon rank sum test for continuous measures (e.g., biomarkers). Due to the relatively small sample size in the study, the adjusted treatment effect of dupilumab will be estimated exploratively in the generalized linear regression for the primary and secondary outcomes to account for the potential impact of patient characteristics (e.g., age, sex, race and co-morbidities). Data transformation will be considered for the outcomes with skewed distribution such as hospital length of stay (LOS) and ICU LOS. The trajectory of each immune biomarker over the follow-up time points will be plotted to characterize the change of immune responses over time, and difference in biomarker (or transformed biomarker to improve normal distribution, if necessary) trajectories between the two study arms will be assessed in the mixed effects model.

Since this is intended to be an early stage, proof of concept study for which the primary goal is to inform future trials rather than to perform formal hypothesis testing, no multiplicity adjustment is planned. In addition, machine learning methods such as random forests algorithm will be applied to fully evaluate the treatment effect and predictability of dupilumab and other important predictors on the outcomes non-parametrically.

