5.3 Secondary outcomes

5.3.1 Eosinophilia as the safety outcome: Eosinophilia is a binary indicator for a patient

to have an absolute eosinophil count $> 0.6 \text{ k}/\mu\text{l}$ at ≥ 1 measurement based on the blood counts with differentials and complete metabolic panels on Day 0, 2, 5, 7, 14, 28 and 60 (Data on Day 7, 28 and 60 would be optional). The outcome will be summarized as the proportion of patients with eosinophilia and the difference in the proportions between the two study arms will be evaluated with Chi-square test. The odds ratio of having eosinophilia for Dupilumab vs. placebo and its 95% CI will also be estimated in logistic regression, with adjustment for other covariates.

5.3.2 Other secondary safety and efficacy outcomes:

- Cumulative incidence rate of adverse events (injection site reactions, eye/eyelid inflammation, conjunctivitis, oropharyngeal pain, insomnia, tooth ache, gastritis, arthralgia, bacterial pneumonia, herpes viral infection, hypereosinophilic syndrome, hypersensitivity reaction, other grade 3 or 4 adverse events, serious adverse events or death) is defined as number of adverse events divided by the total number of individuals in the population at risk for the time interval. The rate ratio of adverse events for Dupilumab vs. placebo and its 95% CI will be analyzed in Poisson regression, in which the follow-up time interval will be considered as the offset. Adjusted analysis for other covariates will be performed, as necessary. Mortality at 60 days will be analyzed as the time to event response. Survival probabilities will be estimated by the Kaplan-Meier method, and the difference in the mortality risk between the two treatment groups will be evaluated by the log-rank test and further in Cox regression, adjusting for the baseline covariates. For the analysis of mortality over the first year, additional adjustment for dynamic mechanical ventilation effect will be considered by including being on ventilation as a time-vary covariate in the Cox regression.
- Plasma total Immunoglobulin E (IgE) levels on Day 0 and 14 will be considered as continuous responses, and difference between treatment arms will be evaluated by t-test or Wilcoxon test initially, and adjusted difference and its 95% CI will be estimated from linear regression. Further, changes of IgE from Day 0 to Day 14 will also be explored and the difference between the two study arms will be analyzed similarly.

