- The response of being alive and free invasive mechanical ventilation at 60 days is a binary response and will be analyzed using the same methods as that for the primary efficacy outcome.
- National Institute of Allergy and Infectious Diseases (NIAID) 8-point ordinal scale on Day 0, 2, 5, 7, 14, 28, 60, 180 and 360 will be considered as longitudinal data. The distributions of the data will be examined visually first and further collapsing will be considered. Collapsed data will be analyzed in the generalized linear mixed effect model or multinomial logistic regression with the generalized estimating equation approach.
- Proportion of patients alive and free of invasive mechanical ventilation at 60, 90, 120, 150, 180, 270 and 360 days will be estimated from the Kaplan-Meier survival for the time to mechanical ventilation-free survival over the first year. The difference in these proportions between the two treatment groups will be evaluated by the log-rank test and further in Cox regression adjusting for the baseline covariates. For the analysis of mortality over the first year, additional adjustment for dynamic mechanical ventilation effect will be considered by including being on ventilation as a time-vary covariate in the Cox regression.
- Need for vasopressors is a binary response and will be analyzed using the same methods as for the primary efficacy outcome.
- Need for renal replacement therapy is a binary response and will be analyzed using the same methods as for the primary efficacy outcome.
- Need for extracorporeal membrane oxygenation (ECMO) is a binary response and will be analyzed using the same methods as for the primary efficacy outcome.

6.0 Other safety analyses:

Analysis of adverse event (AE) data will primarily be descriptive based on CTCAE coding of events. The proportion of subjects experiencing a severe AE and the proportion experiencing a Grade 3 or higher will be recorded. AE will be compared to published data.

7.0 Sample size estimation and power analysis:

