This trial is intended to be an early stage and proof of concept study with the primary goal to collect reliable data and obtain sufficient evidence for future trials. Thus, the emphasis of the study is an exploratory estimation of effect size and incidence of adverse events in terms of eosinophilia; it is not considered as a pivotal trial for efficacy at this time. Therefore, a larger significance level (one-sided alpha=0.1), and the sample size is pre-selected based on the feasibility. Given the current decline trend in the incidence of COVID-19 positive cases, we anticipate to enroll 40 patients realistically into this randomized clinical trial, which shall be sufficient for us to collect reliable and interpretable data for proof of concept to inform future trials. The COVID-19 hospitalization data from our University of Virginia Health System between March 2020 and April 6, 2021 showed that 79.5% of COVID-19 inpatients were alive and free of mechanical ventilation at 28 days under the usual care. With 40 patients that are deemed to be feasible, we would expect Dupilumab to improve a margin of 17.7% in the proportion of patients alive and free of mechanical ventilation at 28 days. That is, it is anticipated that 97.2% of patients being alive and free of ventilation at 28 days in the Dupilumab arm. The power analysis is conducted using the one-sided Score test (Farrington & Manning) with 75% power and 10% type I error.

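### The one-year mortality Cox model may adjust for current ventilation, which dupilumab is meant to prevent, and the SAP does not say which hazard ratio is the treatment effect

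*SAP*

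**What the plan says.** SAP 5.3.2 mentions one-year mortality in two bullets, one on adverse events and mortality and one on ventilation-free survival to day 360. Both carry the same sentence, that for one-year mortality "additional adjustment for dynamic mechanical ventilation effect will be considered by including being on ventilation as a time-vary covariate in the Cox regression".

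The first bullet also covers 60-day mortality: "Mortality at 60 days will be analyzed as the time to event response", using Kaplan-Meier, a log-rank test and a Cox model with baseline covariates. The second bullet plans a log-rank test and baseline-adjusted Cox model for ventilation-free survival.

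These statements bear on the ventilation term:

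- SAP 1.5 excludes "Patients who require invasive mechanical ventilation at time of enrollment".
- SAP 2.1 defines the primary endpoint as a "binary indicator for whether a patient would be alive and free of invasive mechanical ventilation at 28 days".
- SAP 7.0 gives the design assumption: "we would expect Dupilumab to improve a margin of 17.7% in the proportion of patients alive and free of mechanical ventilation at 28 days", from 79.5% to 97.2%.
- Protocol 3.1 reports that "COVID-19 patients with high plasma interleukin (IL)-13 levels have a significantly greater risk of needing mechanical ventilation". Protocol 3.2 says that dupilumab blocks IL-4 and IL-13 signalling.
- SAP 5.1 states: "The difference between dupilumab and placebo arms in outcome measures will be primarily analyzed under ITT principle".

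The SAP does not say what would trigger the ventilation adjustment, which HR is the treatment effect on one-year mortality, or how to read the adjusted one.

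**The concern.** Nobody is invasively ventilated at randomisation, so invasive ventilation is always a post-randomisation event. On the trial's own reasoning it lies between treatment and death. Conditioning on it compares the death hazard of ventilated patients with ventilated, and of unventilated with unventilated. Deaths avoided because fewer dupilumab patients were ever ventilated no longer count in the drug's favour.

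The adjusted HR is also not a safe direct effect. If unmeasured severity drives both ventilation and death, patients ventilated despite an effective drug are sicker on average than ventilated placebo patients. The comparison within ventilation status is then confounded against the drug.

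If the drug works partly by preventing ventilation, the adjusted HR moves towards or past 1 and could be read as no lasting survival benefit. The step is optional, with no trigger and no stated role, so the choice between two HRs could be made after both are seen.

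**Working it through.** **What the plan gives.** The SAP states no HR, event count or power for one-year mortality. Its only design figure is 75% power for the day-28 endpoint (20 per arm, 79.5% v 97.2%, one-sided 10%, score test). Exact enumeration of that test gives 75.1%, so the figure reproduces. It is used here only to calibrate one scenario.

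**The two models.** Let A be arm and V(t) current ventilation.

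- Total effect: h(t) = h0(t) exp(βA)
- As the SAP would consider: h(t) = h0(t) exp(βA + γV(t))

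Suppose the drug changes only the chance of being ventilated. Given V(t), the death hazard is then the same in both arms. The second model gives β = 0 and HR 1.00 however many deaths the drug prevents. That follows from the model; the simulations show how far the total HR lies from 1 and what unmeasured severity adds.

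**Assumed inputs (not in the documents).**

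- Patients may move onto ventilation during days 0 to 28 and stay on it for a mean of 20 days. Follow-up is 365 days.
- The death hazard is 0.0003/day off and 0.02/day on ventilation.
- In scenario 1 the ventilation hazard is 0.010/day, multiplied by 0.4 on dupilumab.
- Unmeasured severity, where included, is a log-normal multiplier (SD 1) on both the ventilation and death hazards.

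**Calibration of scenario 2 (no unmeasured severity).**

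- Control: −ln(0.795)/28 = 0.00819/day; less 0.0003 for death leaves 0.00789/day for ventilation.
- Dupilumab: −ln(0.972)/28 = 0.00101/day; less 0.0003 leaves 0.00071/day.
- Ratio: 0.00071/0.00789 = 0.09.
- With severity (mean 1), the solved values are 0.00934/day and a ratio of 0.08.

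**Results (1,000,000 simulated patients per scenario).**

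| Scenario | Unmeasured severity | Total HR | Ventilation-adjusted HR |
|---|---|---|---|
| 1. Ventilation hazard ×0.4, no other effect | none | 0.77 | 1.00 |
| 1. Same | mean 1 | 0.78 | 1.08 |
| 1. Same | median 1 | 0.77 | 1.11 |
| 2. Calibrated to 79.5% v 97.2% | none | 0.68 | 1.00 |
| 2. Same | mean 1 | 0.64 | 1.14 |
| 3. Death hazard ×0.6, ventilation unchanged | none | 0.62 | 0.60 |
| 3. Same | mean 1 | 0.67 | 0.64 |

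A numerical integration of these scenarios agrees to about 0.01.

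**Other assumed rates.**

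- With a death hazard of 0.04/day on ventilation, a 20.5% control risk of ventilation by day 28 and 2.8% to 15% on dupilumab, simulations of 40,000 patients gave total HRs of 0.57 to 0.85 and adjusted HRs of 0.96 to 0.97. The expected adjusted value is 1.00; the rest is simulation error. With unmeasured severity the ranges were 0.56 to 0.89 and 1.06 to 1.17.
- Adding a direct effect on death (×0.7) to that set, without unmeasured severity, gave total HRs of 0.44 to 0.63 and adjusted HRs of 0.69 to 0.74.

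**Precision.** Protocol 6.2 reports 7 deaths among 40 patients by day 60. SE(log HR) ≈ 2/√7 = 0.76, so a 95% interval runs a factor of exp(1.96 × 0.76) ≈ 4.4 either side. Simulating 40 patients under scenario 1 with median-1 severity (mean 8.7 deaths) gave an SD of the log HR of 0.74 total and 0.82 adjusted.

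**The case against.** The strongest reply is that the ordering can be inferred. In the first bullet the sentence follows the log-rank and baseline-adjusted Cox analyses, the adjustment is called additional, and it is only to be considered. SAP 5.1 says arms are first tested unadjusted and calls adjusted effects exploratory. This helps, but 5.1 refers to generalized linear regression on patient characteristics, not to a Cox model with a post-randomisation covariate. For one-year mortality the base model is inferred from neighbouring sentences.

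Second, a time-varying covariate keeps every patient in the assigned arm, so intention-to-treat is not breached in its narrow sense. That is correct. The difficulty is what the coefficient estimates, not who is analysed where.

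Third, one-year mortality is not listed as an outcome in SAP 2.2, the trial is exploratory with 40 patients, and ventilation-free survival and the ordinal scale run to day 360 without the ventilation term. All of this stands and limits the weight of the point. It does not make the adjusted HR a treatment effect.

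Fourth, the assumed rates are milder than the trial's. The documents give 7/40 = 17.5% dead by day 60; scenario 1 without severity gives 8.3% v 4.6%, and scenario 2 gives 7.0% v 2.3%. The HRs are therefore illustrations, not estimates for this trial. Rates closer to 7 of 40 widened the gap (0.60 v 1.00, and 0.67 v 1.13 with unmeasured severity), so this objection does not shrink the concern.

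Finally, the scenario 1 shift without severity, ln(1.00/0.77) = 0.26, is about a third of the SD of 0.74. One trial of this size could not show it. But SAP 7.0 gives effect-size estimation for future trials as the emphasis, and more patients would not remove the shift.

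**Conclusion.** The concern holds. Used as written, the ventilation term yields an HR that is not the effect of assignment to dupilumab on one-year mortality, and the plan does not name the HR that is. When the drug acts wholly through ventilation, adjustment moves the HR from 0.77 or 0.68 to 1.00, and to between 1.08 and 1.14 with unmeasured severity. When the drug lowers death without affecting ventilation, the change is small and in the other direction (0.62 to 0.60, or 0.67 to 0.64).

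The sizes rest on assumed hazards. The conclusion rests only on ventilation arising after randomisation, which the exclusion criterion guarantees, and on the drug affecting it, which the trial's rationale and primary endpoint presume. The problem is confined to an optional secondary analysis. It should be corrected but does not threaten the main result.

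**What to change.** In both bullets of SAP 5.3.2, remove the time-varying ventilation term from the treatment-effect model. State that one-year mortality is compared by the log-rank test and a Cox model with baseline covariates only, including the randomisation severity stratum (oxygen 15L or less v more than 15L, SAP 1.4).

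If a ventilation-adjusted model is kept, label it exploratory, state its assumptions, including no unmeasured common causes of ventilation and death, and do not report its HR as the treatment effect. No further model is needed, because ventilation-free survival and the ordinal scale already describe the course through ventilation.

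The cost is one sentence changed in two places, with no new data or enrolment. The Protocol reports enrolment as closed and 60-day mortality as known, so the change should be a dated amendment that says so.

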8.0 Missing data

Since patients in this study will be closely followed for mortality and status on mechanical ventilation, the primary outcome of being alive and free of ventilation is likely captured. Dropout from the study will be carefully evaluated for its potential informativeness. A sensitivity analysis will be performed to examine the impact on the proportion and its confidence limits. In particular for the primary endpoint, individuals who withdraw will be considered events if their statuses on day 28 are unknown.

Other outcome variables (clinical conditions and laboratory biomarkers) will have missing data due to dropout from treatment and/or from study participation, or due to missed outpatient visits if patients have been discharged from the hospital. The generalized linear model, or mixed effects model frameworks that will be used for analyses, works with what data are gathered, and assumes missing data are missing at random. For selected secondary outcome analyses, sensitivity analyses will be considered to examine the stability of estimated treatment effects in the face of departures from the assumption of missing at random.
